The dramatic advances in sensing technology and miniaturization have reached a stage at which it is now possible to: 1) put electromagnetic, optical and impedance technologies into small adhesive “dots” on the skin, 2) stream data from multiple anatomic locations, and 3) algorithmically transform these data such that the system alarms when it recognizes patterns suggestive of ongoing hemorrhage. We have been developing such a system, one that combines state-of-the-art noninvasive sensing technologies and advanced multivariable statistical algorithms. This system will be developed from its inception to be inexpensive and easily applied, even in austere settings.

Progress to Date: In years I and II the project made excellent progress in development of this technology. Using pre-existing data sets, we developed preliminary multivariate algorithms. We then developed a low-volume occult hemorrhage porcine model and utilized it for evaluation of a broad ensemble of noninvasive technologies and further development of the diagnostic/predictive algorithm.

We have successfully developed a sophisticated multivariate ML algorithm that provides superior performance at detecting/predicting bleed/no-bleed in occult hemorrhage and LBNP. The average ROC-AUC values are in the range of 97% 20-25 min. into our porcine low-volume occult hemorrhage model. This accuracy is far superior to all prior studies and better than our expectations at the start of the project with respect to what we anticipated being able to achieve at this stage of the project. We have successfully identified the principal drivers of this high accuracy: the largest contribution comes from the features generated from the raw impedance tomography signals, which in-and-of-themselves are able to provide an AUC value of higher than 80% on a consistent basis.

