In summary: we have developed a promising multi-technology poly-anatomic approach to development of noninvasive sensing in the setting of occult hemorrhage. The year one and year two studies used a rack system composed of commercial impedance and optical components. After evaluating the performance of individual components, we have been able to “prune” the court technologies to: impedance tomography, impedance spectroscopy, NIRS, plethysmography and ECG. The impedance and optical technologies have been incorporated into a first-generation prototype.

Phase III Trauma Validation and Re-Training Trial

Approach/Methods

Summary: We will enroll 480 trauma patients in a “no significant risk” prospective clinical trial to: 1) evaluate the performance of our Mark I prototype, 2) validate the performance of the Phase II algorithm and 3) re-train the algorithm to Phase III iteration.

This is not a therapeutic study. All technologies are non-invasive.

The main outcome variables are non-invasive measurements that will be used for machine learning, not real-time patient management. The data generated will be used later for discovery and validation in traditional and innovative machine learning.

Inclusion criteria:

1. Age ≥ 18
2. Patients suffering blunt and/or penetrating trauma
3. Awake and alert with GCS ≥ 14 as indicated by the treating provider/care team
4. Triage systolic blood pressure greater than 90 and heart rate less than 120

Exclusion criteria:

1. Need for ongoing fluid or pressor support (standard local fluid resuscitation only)
2. Signs of clinically significant ongoing external hemorrhage with active bleeding documented on radiology/ultrasound during initial evaluation (approximately 15 minutes post ED arrival)
3. Respiratory distress with O₂ saturation <96%
4. Pre-existing systemic illness, likely to alter systemic cardiovascular response to hemorrhage (overt clinical heart failure). Including congestive heart failure, and a paced cardiac rhythm.
5. Pregnant
6. Prisoner status
7. Anatomical abnormality or injury that would prevent placement of the electro-optical electrodes

Screening and Enrollment: The study team will approach ED patients initially evaluated by the Trauma team/ED care team in the Trauma room and currently being observed in a general ED bed who had met inclusion criteria. Those patients will participate in the informed consent process with study personnel following departmental and hospital SOP.

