As a minimal risk study, there will be no change in the routine care of these patients.

Definition of hemodynamic deterioration - any of:

- A significant period (greater than 5 min.) of systolic blood pressure less than 90 associated with a heart rate greater than 110.
- 20% increase in HR from baseline
- 15% decrease in MAP from baseline
- Clinician defined need for greater than established initial fluid resuscitation (blood products intended to maintain blood pressure)
- A blood lactate result greater than 4 without nontraumatic causes of lactic acidosis

Study Design: Prospective Case Cohort

- Screening for enrollment will be undertaken in the Emergency Department (ED).
- Patients will be assigned a de-identified Research **Subject Number**
- Please note that at the discretion of the clinical study team, less than the complete ensemble of noninvasive sensing technologies may be utilized in specific cases based on patient comfort and clinical circumstances.

Placement of Sensing Technologies

[figure not shown]
- After confirmation of inclusion criteria, the absence of exclusion criteria, and informed consent is documented, trained research personnel will apply all sensors described below to appropriate locations on the patient's skin.
- Patients will already have undergone application of the ECG and pulse ox plethysmography disposables as part of normal clinical monitoring. These will be left in place and the ECG and plethysmography data will be shared with our prototype data collection system in a manner that does not interfere with the clinical monitor electrodes. The study monitor data will be acquired via iCollect software manufactured by GE. The software collects biometric data (e.g. EKG, SpO2) from clinical monitors without any imbedded PHI.

- Two SwissTom EIT arrays will be placed per subject: 1) around the thorax at the anatomic nipple line, and 2) the second alternating patient to patient between the upper abdomen at the level of the liver-spleen and the proximal thigh at the femur mid-shaft.
- **NIRS** – 3 locations, 1 probe per location: upper chest in region of thoracic EIT, and 1 either upper thigh or upper arm.
- Three sets of four ScioSpec EIS electrodes (I+, V+, V-, I-). V electrodes are placed medially to I electrodes.
 - 1st set – is applied on the torso just above the upper SwissTom arrays, I+ and V+ on the right mid-axillary line and V- and I- on the left mid-axillary line.

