 - 2nd set – is applied between the upper and lower SwissTom arrays adopting the same positioning technique as set one with respect to the mid-axillary line. In patients with the 2nd SwissTom array on the thigh, the 2nd ScioSpec EIS is also applied in this same truncal location.
 - 3rd set – applied on the right upper arm, “+” leads on the outside of the arm and “-“ leads on the inside, sandwiching the bicep.
- Please see device descriptions on pg. 12 for further detail

System Setup

CLINICAL MONITOR		
1. Clinical monitor: Open the desktop icon “iCollect - shortcut”	 iCollect - Shortcut	

2. At the following menu, ensure the settings in the orange box are as shown below and click “Online”

Patient Case Methods

- Research team member will turn on device and enter study identifier data.
- Research team member applies the device sensors as per Appendix II
- Research team member will confirm that data is being acquired.
- Device will remain attached to each patient until any of the following:
 - Stable for 6 hours (no signs of hemodynamic deterioration)
 - Disposition via discharge from the ED or admission to a care unit
 - Development of change from baseline hypotension or tachycardia below or above limits respectively.
 - The patient wishes for the device to be removed.
- The following data will be collected from the sensors: heart rate and electrical activity via electrocardiogram, transcutaneous oxygen saturation, blood pressure and arterial waveforms via finger plethysmography. Lastly, sensor data will collect changing perfusion physiology via electrical impedance tomography system.
- The study coordinator will extract relevant data from the patient's chart to complete a case enrollment form.
 - Data points from chart-
 - Gender

- Age (by decade)
- Height
- Weight
- Medications given during the ED visit and admission (if patient is admitted)
- Vital signs at triage and at “change in status.”
- Based on clinical chart review, the PI and co-PI will independently adjudicate each patient into either the “likely ongoing hemorrhage” or “likely no ongoing hemorrhage” outcome categories without reference to the algorithm results. In the event of differing results, the PI and the co-PI will meet and discuss until consensus is reached.
- At the quarterly milestones the existing data will be used iteratively to refine the Phase II algorithm, creating an initial Phase III algorithm.

Data Acquisition and Storage:

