SwissTom Impedance Tomography, NIRS Spectroscopy and ScioSpec Bioimpedance raw signals are all stored in a live, streaming fashion directly on an internal hard drive. All of this data is non-PHI and completely de-identified – only the subject number is incorporated into the file name. Similarly, any data collected by iCollect (mentioned above) has absolutely no PHI embedded within it and is live-captured and saved on an internal hard drive. At the end of the experiment all of this non-PHI, de-identified data will be uploaded to a secure cloud-based drive that has been approved by the participating institutions.

Data Analysis

At the completion of the study, the full data set will be used to define the performance of the Phase II algorithm with respect to the pre-specified performance criteria.

Data analysis will include the following steps:

- 1) **Data cleaning, filtering and validation:** All data will be processed to ensure that patterns are consistent with the underlying physiology. Any physiologically incorrect data will indicate issues related to loose electrodes, malfunctioning sensors,

etc. Such data will be filtered and cleaned to ensure that only meaningful data is used for algorithm testing.

- 2) **Data transformation and feature generation:** The cleaned, validated data will be transformed through a series of processing steps to generate the necessary features to be used in the supervised machine learning algorithms as predictors.
- 3) **Classification:** The features will then be used to generate machine learning-based predictions. These predictions will be compared against the ground reality of the patient's status to evaluate the algorithm performance.

Algorithm Performance Criteria: the algorithms developed will be trained to alarm under two circumstances indicating significant risk of ongoing hemorrhage progressing to shock: 1) a change from baseline, 2) development of prespecified patterns.

Performance will be judged on the basis of:

1. time of alarm before onset of deterioration
2. sensitivity, specificity, PPV, NPV for alarm/no alarm outcome
3. ROC curve and AUC for alarm/no alarm outcome
4. false-positive and false-negative rates

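### Accuracy measures and re-training have no signal cut-off at fluid or blood treatment, so treatment effects can distort the Phase II result in either direction and enter the Phase III algorithm

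*Combined protocol and SAP*

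**What the plan says.** Under Definition of hemodynamic deterioration, one qualifying event is "Clinician defined need for greater than established initial fluid resuscitation (blood products intended to maintain blood pressure". A raised lactate is another.

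Patient Case Methods gives four reasons for removing the device. Three are six hours of stability, the end of the ED stay (whether the patient goes home or to a ward), and the patient's wish. The remaining one is "Development of change from baseline hypotension or tachycardia below or above limits respectively". Neither fluid, blood nor lactate is named. Of routine care, the protocol says "there will be no change in the routine care of these patients", so clinicians may treat while the device records. Exclusion criterion 1 reads "Need for ongoing fluid or pressor support (standard local fluid resuscitation only", which appears to allow standard initial fluid before entry.

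On the predictor, Progress to Date reports that in the porcine model "the largest contribution comes from the features generated from the raw impedance tomography signals".

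On the label, two investigators review the chart and place each patient as likely or not likely to have ongoing hemorrhage. They do so without sight of the algorithm's output, but nothing hides treatment from them.

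On the analysis, Data Analysis says "These predictions will be compared against the ground reality of the patient's status to evaluate the algorithm performance" and applies this to all collected data. The Algorithm Performance Criteria allow an alarm on a change from baseline. They list lead time before deterioration, then sensitivity, specificity, PPV, NPV, ROC/AUC and error rates. Patient Case Methods adds quarterly refinement of the algorithm on the data accrued so far.

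**The concern.** The device is meant to warn while bleeding is still occult, before anyone has acted. The plan allows signal recorded after clinicians have acted to count in most accuracy measures and in training. Clinicians are likely to give volume mainly to patients they suspect are bleeding, and the adjudicators see that treatment in the chart. If the infusion also changes the sensor signal, predictor and label share a cause that is not hemorrhage: the clinician's suspicion.

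Two results are at stake. The validation of the Phase II algorithm may not describe its performance in untreated patients. The Phase III algorithm may learn what resuscitation looks like, which is absent in the setting where the device is needed. Blinding clinicians to the device does not break this link, because the information passes from treatment to signal and from treatment to label.

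**Working it through.** **1. The two lists side by side.** Extra fluid or blood is a deterioration event and is not a removal trigger. Read literally, a patient who meets that criterion also no longer satisfies the six-stable-hours trigger. Recording then ends only at disposition, at hypotension or tachycardia beyond limits, or at the patient's request. Continued recording follows from what the removal list omits; the protocol does not state it.

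**2. What is anchored in time.** Lead time is. Sensitivity, specificity, PPV, NPV, AUC, error rates and re-training are not: no scoring window is given. Data cleaning targets loose electrodes and faulty sensors, so a physiologically valid response to an infusion would pass. The case form lists medications given; fluids, blood and start times are not named.

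**3. The plan's own figure.** The plan gives 480 patients and p < 0.05 for ROC-AUC, with no prevalence, target AUC or power. The 480 cannot be reproduced, and this point does not dispute it.

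**4. Size, under assumed inputs.** None of these inputs is in the documents.
- f = share of bleeders treated within the scored recording: 25%, 50%, 75%
- g = the same share in non-bleeders: 5%
- s = shift of the alarm score caused by treatment: +1 or −1 SD
- Scores are normal with SD 1. Untreated bleeders and non-bleeders differ by d = √2·Φ⁻¹(true AUC).

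Observed AUC = [(1−f)(1−g) + fg]·Φ(d/√2) + (1−f)g·Φ((d−s)/√2) + f(1−g)·Φ((d+s)/√2).

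For a true AUC of 0.70, d = 1.414 × 0.5244 = 0.742, Φ((d+1)/√2) = 0.891 and Φ((d−1)/√2) = 0.4275. With f = 50% and s = +1:

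(0.475 + 0.025) × 0.70 + 0.025 × 0.4275 + 0.475 × 0.891 = 0.350 + 0.011 + 0.423 = 0.784.

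| True AUC | s | f = 25% | f = 50% | f = 75% |
|---|---|---|---|---|
| 0.70 | +1 | 0.74 | 0.78 | 0.83 |
| 0.70 | −1 | 0.64 | 0.58 | 0.51 |
| 0.50 | +1 | 0.55 | 0.62 | 0.68 |
| 0.50 | −1 | 0.45 | 0.38 | 0.32 |

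If more non-bleeders are treated, the distortion shrinks: with f = 50% and g = 20%, a true 0.70 reads 0.75 (s = +1) or 0.61 (s = −1). With f = g = 50% it reads 0.68 for either sign.

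**5. Against the plan's criterion.** Take p < 0.05 as a two-sided test against AUC 0.5, with null SE = √[(m+n+1)/(12mn)] for m bleeders and n non-bleeders. At an assumed 10% prevalence (m = 48, n = 432), SE = √(481/248,832) = 0.044, so significance needs 0.5 + 1.96 × 0.044 = 0.586. At 5% (m = 24, n = 456), SE = √(481/131,328) = 0.0605 and the threshold is 0.619. A treatment-only AUC of 0.68 exceeds both thresholds. The 0.62 (0.617 unrounded) exceeds the first and just misses the second. The 0.55 exceeds neither.

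**The case against.** The strongest reply is that the first performance criterion already protects against this. Need for extra fluid or blood is itself deterioration, so if onset is dated at that decision, an alarm provoked by the infusion comes too late to earn lead time. That stands for lead time. It does not cover standard initial fluid, and it does not reach the other measures or the re-training.

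A reader might infer that accuracy is necessarily inflated. The documents do not support that. The Phase II algorithm was developed on volume loss, and volume replacement could mask its pattern as easily as mimic it; the −1 SD rows show the effect.

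A reader might also take the Progress to Date remark on impedance and TFC as proof that infused fluid moves the tomography signal. That sentence concerns a different, bioimpedance-cardiography device, and TFC is not defined. That infusion moves the study signal is physiological reasoning, and the ranking of tomography as main contributor comes from pigs.

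Exposure is also uncertain. Hypotension, tachycardia or admission may end many recordings first. A baseline taken during a bolus fits poorly with exclusion criterion 1 and with enrolment from a general ED bed after the initial evaluation; a baseline just after a bolus remains possible.

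Finally, cutting the record at treatment has its own bias. It shortens recordings mainly in suspected bleeders, leaving them less time to alarm and lowering sensitivity. That objection stands, and the remedy has to allow for it.

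**Conclusion.** The gap is real and should be closed. As written, on-treatment signal can count towards every accuracy measure except lead time and can be used for re-training, against a label that is not blinded to treatment. The direction of bias for the Phase II algorithm is unknown. Under the stated assumptions a true AUC of 0.70 could read anywhere from 0.51 to 0.83, and an algorithm with no hemorrhage information could read 0.55–0.68 if treatment raises its score. These figures illustrate sensitivity to assumed treatment rates and an assumed 1 SD shift; they do not estimate the bias in this trial. If few patients are treated while recording, or if infusion does not move the signal, the effect is small. The plan requires nothing that would show which case applies. The re-training concern does not depend on direction, since a supervised algorithm can learn a treatment signature of either sign.

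**What to change.** - Extract from the chart the start time of each fluid bolus, blood product and vasoactive drug given while the device is on, and align these times with the signal files.
- Base the main test of the Phase II algorithm, and Phase III training, only on signal before the first such post-baseline treatment or deterioration onset, whichever is earlier. Report the whole-record result as a sensitivity analysis.
- Report recording length by label, and compare bleeders and non-bleeders over matched time windows, to deal with the shorter records in suspected bleeders.
- Flag patients whose initial bolus had just finished at baseline, and report results with and without them.
- The sponsor should reconcile the deterioration list with the end-of-recording list in Patient Case Methods, so that each event type has a defined last usable time point.

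Patient care does not change. The cost is some added chart extraction, which the coordinator's existing case form can carry, and analysis wording. There will be less usable signal, and the accuracy figures may be less favourable or less precise. It is best done before further quarterly re-training, since each round can build on-treatment signal into the algorithm.

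### Scoring is offline and no rule limits each processing step to data already recorded, so the reported alarm lead time may differ from what a bedside device could give

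*Combined protocol and SAP*

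**What the plan says.** The Approach/Methods summary makes the algorithm work retrospective: "The main outcome variables are non-invasive measurements that will be used for machine learning, not real-time patient management", and "The data generated will be used later for discovery and validation in traditional and innovative machine learning". Appendix II describes starting four acquisition programs (clinical monitor, EIS, EIT, NIRS) and no alarm program, so alarm times are computed from stored files.

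The Data Analysis section sets the time of scoring: "At the completion of the study, the full data set will be used to define the performance of the Phase II algorithm". Three steps follow.

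- Step 1, cleaning: "All data will be processed to ensure that patterns are consistent with the underlying physiology". It reaches the test data: "Such data will be filtered and cleaned to ensure that only meaningful data is used for algorithm testing".
- Step 2, features: "The cleaned, validated data will be transformed through a series of processing steps to generate the necessary features".
- Step 3, classification: predictions from those features are compared with the patient's actual status.

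Under Algorithm Performance Criteria, the first item is "time of alarm before onset of deterioration". Sensitivity, specificity, predictive values, ROC/AUC and error rates come after it. One of the two alarm triggers is a change from baseline.

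The plan gives no filter type, window length, scaling reference, baseline period or rule for time-stamping an alarm. It does not say whether a step may use samples recorded after the time being scored.

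Two other provisions bear on the point. Under Data Acquisition and Storage, the "raw signals are all stored in a live, streaming fashion directly on an internal hard drive". Under Patient Case Methods, recording can end when hypotension or tachycardia develops; otherwise it ends at six stable hours, at disposition or at the patient's request.

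**The concern.** The Background describes an automated system that watches stable patients continuously. Such a system has only past data when it decides to alarm. An offline analysis holds the complete file, and common processing steps use it by default: smoothing centred on t, zero-phase filtering, scaling by the mean and SD of the recording, or rejecting a segment because of what follows it. Each puts later information into an output dated t. This is separate from the question of which data are discarded, since smoothing and scaling can do it with nothing removed.

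Lead time is the measure most directly exposed, because it depends on when the output crosses a threshold. A lead time that relies on later samples does not measure the intended use. There is a second route. Because a recording can stop at deterioration, its length and its whole-file summaries can carry outcome information, which could distort sensitivity, specificity and AUC too.

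**Working it through.** The plan states no lead time, target or window, so there is no figure to reproduce. The check asks how far, and in which direction, unstated time direction could move the result. All simulation inputs are assumptions, not trial figures.

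**1. Centred versus trailing smoothing**

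Inputs: 1-minute samples; independent noise with SD 1; signal flat to minute t0 = 60, then rising at b = 0.1 SD/min; deterioration at minute 110; alarm when the moving average exceeds h = 2 SD; 2,000 recordings per window W.

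On a linear ramp, ignoring noise:

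- A centred average crosses at t0 + h/b = 60 + 2/0.1 = minute 80, so lead = 110 − 80 = 30 min.
- A trailing average lags by (W − 1)/2 and crosses at 80 + (W − 1)/2.
- The gain from centring is (W − 1)/2.

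| Window (min) | (W − 1)/2 | Mean lead, trailing | Mean lead, centred | Gain |
|---|---|---|---|---|
| 5 | 2 | 29.5 | 31.5 | 2.0 |
| 11 | 5 | 24.8 | 29.8 | 5.0 |
| 21 | 10 | 19.6 | 29.6 | 10.0 |
| 31 | 15 | 14.5 | 29.5 | 15.0 |

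A second simulation used a 4 SD ramp over the 60 min before onset, AR(1) noise, an alarm at 2 SD, and 1,500 bleeds and 1,500 non-bleeds per window. Mean lead, centred versus trailing, was 37.5 v 35.6 min (5-min window), 31.3 v 27.3 (10-min) and 29.6 v 19.6 (21-min): gains of 1.9, 4.0 and 10.0. False-alarm probabilities in non-bleeds were 0.059 v 0.061, 0.001 v 0.001 and 0 v 0. Without a trend the two averages behave alike, so the gain brings no extra false alarms.

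**2. Whole-recording versus baseline-only scaling**

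Inputs: the ramp from step 1, an 11-min trailing filter (lag 5 min), alarm at a standardised value of 1.

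- Scaled on the first 40 min (mean 0, SD 1): raw threshold 1; crossing at 60 + 1/0.1 + 5 = 75; lead 35 min. Simulated: 35.5.
- Scaled on all 110 samples: the ramp takes values 0.1k for k = 1 to 49. Mean = 0.1 × 1,225/110 = 1.114. Mean square = 0.01 × 40,425/110 = 3.675. Variance = 3.675 − 1.114² + 1 (noise) = 3.43, SD 1.85. Raw threshold = 1.114 + 1.85 = 2.97; crossing at 60 + 29.7 + 5 = 94.7; lead 15.3 min. Simulated: 15.3.

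Here look-ahead shortens the lead by about 20 min, because the ramp inflates the recording's own mean and SD. The opposite can also occur. If the baseline stretch is noisier than the rest, for example while electrodes settle, a whole-recording SD can be smaller than the baseline SD and the alarm comes earlier. That case was reasoned through, not simulated.

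**3. Effect on the other criteria**

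A further run used a 4 SD ramp over 60 min, AR(1) noise, an 11-min trailing filter and an alarm at 1.5, with whole-recording scaling in place of subtracting a first-20-min baseline. False alarms moved from 0.32 to 0.23 with a 60-min flat period and from 0.54 to 0.63 with a 240-min one. Sensitivity in the 60-min case fell from 0.997 to 0.88.

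**The case against.** The strongest reply is that the plan is silent, and silence is not a defect. Clean, transform, classify describes any pipeline, including one that uses only past data. The reference to all data, and to the full data set at study completion, most naturally means every subject's data, not each recording taken end to end. Both alarm triggers, a change from baseline and the development of set patterns, suit forward detection. The Phase II algorithm already exists, its specification is not part of this document, and filter direction would normally sit there. The study collects data and develops an algorithm; no patient is managed on the alarm.

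Much of this stands. A reader might infer that processing is run on whole recordings and that the lead time is therefore overstated. The documents support neither statement: they do not say that any step uses later samples, and step 2 of the check shows that look-ahead can also shorten the lead. A reader might also infer that no other listed criterion would show the problem. That holds for centred against trailing smoothing only; whole-recording scaling moved both sensitivity and false alarms. Finally, the 20-25 min in the Background's progress report is time into the porcine bleed at which AUC was assessed, not lead time before deterioration, so it cannot show whether a gain of a few minutes is large.

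What does not stand is the suggestion that the matter can be left to an unseen specification. This document defines the performance assessment and names lead time first, yet as written an alarm time that no bedside device could produce would comply with it.

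**Conclusion.** The point holds as a gap in the scoring rule. Scoring is offline, cleaning reaches the test data, lead time is a named criterion, and nothing holds each step to data recorded up to the time scored. The reported lead time may therefore differ from bedside performance.

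The size depends on steps that the plan does not specify. Centred smoothing would add about half the window: about 2 min for a 5-min window, 5 for 11 and 10 for 21, with no more false alarms. Whole-recording scaling could move lead time in either direction, by about 20 min downward in one assumed case, and could change sensitivity, specificity and AUC. These figures rest on assumed ramps, noise, thresholds and windows; they show mechanism and scale and do not predict this trial's result.

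The rule should be settled before scoring. The gap does not impair data collection, and because the raw signals are kept it can be closed without new patients.

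**What to change.** Add to Data Analysis, step 3:

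- All primary performance results come from a past-only replay of the stored raw streams, with code frozen before scoring.
- At each time t, artefact rejection, filtering, scaling, baseline and features use only data recorded up to t.
- Each alarm is stamped at the time its output would have been available, including window and processing delay.
- Periods rejected in the replay give no output, and their frequency is reported.
- Features based on the whole recording or on its length are not allowed.
- Batch-processed results may be shown as secondary.

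The cost is some recoding of the processing pipeline. The stated lead time may turn out shorter, but it would be one that a bedside device could reach.
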